8.1.3. Deaths, Serious Adverse Events, and Survival Status

In addition to the tabular summaries of AEs described in Section 8.1.2, listings for all SAEs [L13.08, L23.08], all deaths [L13.09, L23.09] and all non-fatal SAEs [L13.10, L23.10] will be produced (which will also identify on study events). The categorization of the cause of death will be adjudicated by GSK.

A listing of reasons for considering an AE as serious will be provided [L13.11, L23.11].

A summary of Serious Adverse Events including Exposure-Adjusted Incidence Rates will be produced for Year 1 On Treatment (Section 5.12) [T13.46] and Years 1&2 combined

On Study (Section 5.11) [T23.38]. These will present Serious Adverse Events Overall and by System Organ Class and Preferred Term and will display:

- the number of subjects experiencing the event (n);
- For Year 1: the sum of the total time to the first event or total on treatment time* if no event (years) across all subjects (e), * defined in Section 15.6.2: On Treatment Exposure (Year 1);
- For Years 1&2 combined: the sum of the total time to the first event or total on-study time* if no event (years) across all subjects (e), * defined in Section 15.6.2: On-Study Exposure (Years 1&2 Combined);
- the exposure adjusted subject rate per 100 subject years ($r = (n/e)*100$).

A summary of Deaths including Exposure-Adjusted Incidence Rates will be produced for Year 1 On Treatment (Section 5.12) [T13.47] and Years 1&2 combined On Study (Section 5.11) [T23.40]. These will present Deaths Overall and by Category and Preferred Term and will display:

- the number of subjects experiencing the event (n);
- For Year 1: the sum of the total time to the first event or total on treatment time* if no event (years) across all subjects (e), * defined in Section 15.6.2: On Treatment Exposure (Year 1);
- For Years 1&2 combined: the sum of the total time to the first event or total on-study time* if no event (years) across all subjects (e), * defined in Section 15.6.2: On-Study Exposure (Years 1&2 Combined);
- the exposure adjusted subject rate per 100 subject years ($r = (n/e)*100$)

Survival status will also be summarized at Weeks 52 and 104. The number and percentage of subjects will be summarized for each of the following categories for Year 1 and Year 1&2 [T13.30, T23.29].

- Alive
- Consent Withdrawn
- Lost to Follow-up
- All Deaths based on the date of death relative to the planned or actual Week 52 visit.
 - For Year 1 reporting, include deaths that occur at or prior to the observed Week 52 visit.
 - For Year 2 reporting (after the actual Week 52 visit):
 - Include all deaths

8.1.4. Adverse Events of Special Interest Analyses

To ensure consistency across belimumab studies, AESI will be defined per the version of the PSAP and MedDRA in effect at the time of DBR.

The Benlysta Program Safety Analysis Plan (PSAP) has been developed to include an adverse event of special interest (AESI) analysis for consistent reporting across belimumab studies. Categorizations for the AESIs are defined in the PSAP.

The milestone defined in the PSAP (i.e. before database release) for adjudications will be “primary analysis database release” (Year 1) and “end of study database release” (Year 2).

Events with a start date on or prior to the week 52 visit date will be attributed to Year 1; otherwise events will be attributed to Year 2. Events will only be reported once even if the event does not resolve by the Week 52 visit.

An overall summary of AESIs will be presented and each specific category of AESI will be presented separately by PT. The number and percentage of subjects with at least one occurrence and the number of events of the following AESIs will be provided [On Treatment: T13.31; On Study: T23.30].

A summary of AESI including Exposure-Adjusted Incidence Rates will be produced for Year 1 On Treatment (Section 5.12) [T13.48] and Years 1&2 combined On Study (Section 5.11) [T23.xxx]. These will present AESI Overall and by each specific category and Preferred Term and will display:

- the number of subjects experiencing the event (n);
- For Year 1: the sum of the total time to the first event or total on treatment time* if no event (years) across all subjects (e), * defined in Section 15.6.2: On Treatment Exposure (Year 1);
- For Years 1&2 combined: the sum of the total time to the first event or total on-study time* if no event (years) across all subjects (e), * defined in Section 15.6.2: On-Study Exposure (Years 1&2 Combined);
- the exposure adjusted subject rate per 100 subject years ($r = (n/e)*100$).

The following AESI will be identified and adjudicated as detailed in the PSAP.

| |
|--|
| Adverse Events |
| Adverse Events of Special Interest (AESI) |
| AESI will be defined per the version of the PSAP/MedDRA in effect at the time of DBR. |
| Malignant Neoplasms |
| 
 • Malignancies Excluding non-melanoma skin cancer (NMSC) • Malignancies Including NMSC 
 • Solid Tumour • Hematologic |

| Adverse Events |
|---|
| Adverse Events of Special Interest (AESI) |
| 
 • Skin (All) 
 • NMSC • Excluding NMSC • Tumours of unspecified malignancy adjudicated as malignant per GSK 
Post-Injection Systemic Reactions (PISR)
 
 • PISR per Anaphylactic Reaction Customized MedDRA Query (CMQ) narrow search • PISR per Anaphylactic Reaction CMQ broad search • PISR per Anaphylactic Reaction CMQ algorithmic search • Serious Anaphylaxis per Sampson Criteria per GSK adjudication • Serious Acute PISR/Hypersensitivity Per GSK adjudication 
 – Serious Acute PISR Excluding Hypersensitivity per GSK adjudication – Serious Acute Hypersensitivity Reactions per GSK adjudication • Serious Delayed Acute Hypersensitivity Reactions per GSK adjudication • Serious Delayed Non-Acute Hypersensitivity Reactions per GSK adjudication 
All Infections of Special Interest (Opportunistic Infections (OI), Herpes Zoster (HZ), Tuberculosis (TB), And Sepsis; All and Serious, separately)
 
 • All opportunistic infections (OI) per GSK adjudication • OI per GSK adjudication excluding Tuberculosis and Herpes Zoster • Active Tuberculosis 
 – Non-Opportunistic – Opportunistic • Herpes Zoster 
 – Non-Opportunistic – Opportunistic 
 ▪ Recurrent ▪ Disseminated • Sepsis 
Depression (including mood disorders and anxiety)/suicide/self-injury (All and Serious, separately)
 
 • Depression (including mood disorders and anxiety) (excluding suicide and self-injury) • Suicide/self-injury • Serious suicide/self-injury per GSK adjudication 
 – Suicidal Behavior 
 ▪ Completed Suicide – Suicidal Ideation – Self-injurious Behavior without Suicidal Intent 
 • Deaths |

Malignant neoplasm events identified as “tumours of unspecified malignancy” will be reviewed for classification as malignant per GSK adjudication and will be presented by category and PT [On Treatment: T13.32; On Study: T23.31].

Post-injection systemic reactions and serious post- injection systemic reactions will be presented using nine different definitions as indicated above. These will be presented by category and PT [On Treatment: T13.33, T13.34; On Study: T23.32, T23.33].

Infection AESIs will be presented by Category and PT for all infections and for infections leading to study treatment discontinuation [On Treatment: T13.41, T13.42; On Study: T23.34, T23.35].

Depression, suicide and self-injury as defined in the PSAP will be presented by Category and PT [On Treatment: T13.43; On Study: T23.36].

All AESI will be presented in a listing [L13.12, L23.12]. Post-Treatment AESIs will be summarized and presented by Category.

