Randomization and the first dose of belimumab should be completed within 35 days of initiation of screening procedures. Participants will be receiving stable standard therapy at entry. At randomization, participants will be stratified by their screening SLEDAI-2K score (≤9 vs. ≥10), by immunosuppressant use at screening (immunosuppressant use vs. no use) and by screening corticosteroid dose (prednisone equivalent ≤10 mg/day vs. >10 mg/day). Belimumab will be administered SC on Day 1 and then weekly (i.e., every 7 days ±1 day) through Week 51 for Arms A and B, and through Week 103 for Arm C. SC injections will be administered at alternating injection sites between the left or right thighs and the abdomen. Rituximab-placebo or rituximab will be administered by intravenous (IV) infusions at Weeks 4 and 6 for Arms A and B. Participants in Arms A and B will be administered a pre-medication regimen 30 minutes before each rituximab-placebo or rituximab infusion on Weeks 4 and 6, including methylprednisolone 100 mg IV or equivalent, an antihistamine, and acetaminophen or equivalent.

Participants in any arm who are deemed treatment failures for efficacy endpoints at any time during the study will be encouraged to remain in the study and continue to have all efficacy and safety assessments.

Participants randomized to Arms A or B who enter the study on immunosuppressants will discontinue immunosuppressants prior to or on the day of the Week 4 visit. Continuing the stable immunosuppressant dose until Week 4 allows participants to receive 3 weeks of belimumab SC prior to discontinuing their immunosuppressants. Corticosteroids may be adjusted as necessary during this transition period. If participants in Arms A and B receive immunosuppressants after the Week 4 visit they will be deemed treatment failures. Participants in Arm C will continue their stable immunosuppressants throughout the study at the discretion of the investigator. If participants in Arm C require an increased dose of their stable immunosuppressant after Week 12 or addition of a new immunosuppressant they will be considered a treatment failure.

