| 23.25. | NEW | ITT | Study Treatment Related Serious Fatal and Non-Fatal Adverse Events by PT – Both Belimumab and Rituximab [1] - On Study (Year 1&2) | 
 New output (required for Plain Language Summary) |
| Survival Status | | | | |
| 23.26. | 23.29 | ITT | Survival Status at Week 104 | |
| Adverse Events of Special Interest (AESI) | | | | |
| 23.27. | 23.30 | ITT Year 2 | Adverse Events of Special Interest by Category - On Study (Year 2) | 
 Use new 'ITT Year 2' Population defined in Section 2.2. |
| 23.28. | NEW | ITT | Adverse Events of Special Interest by Category - On Study (Year 1&2) | 
 New output (omission in original RAP) |
| 23.29. | 23.31 | ITT | Malignant Neoplasm Adverse Events of Special Interest by Category and PT - On Study (Year 1&2) | 
 Now presents data for Year 1&2 |
| 23.30. | 23.32 | ITT | Post Belimumab SC Injection Systemic Reactions Adverse Events of Special Interest by Category and PT - On Study (Year 1&2) | 
 Now presents data for Year 1&2 |
| 23.31. | 23.33 | ITT | Serious Post Belimumab SC Injection Systemic Reactions Adverse Events of Special Interest by Category and PT - On Study (Year 1&2) | 
 Now presents data for Year 1&2 |

| Safety Tables | | | | |
|---|-------------------|------------|---|--|
| New output number | Old output number | Population | Title | Major modifications since original RAP |
| 23.32. | 23.34 | ITT | Infection Adverse Events of Special Interest by Category and PT - On Study (Year 1&2) | 
 • Now presents data for Year 1&2 |
| 23.33. | 23.35 | ITT | Infection Adverse Events of Special Interest Leading to Belimumab SC Study Treatment Discontinuation by Category and PT - On Study (Year 1&2) | 
 • Now presents data for Year 1&2 |
| 23.34. | 23.36 | ITT | Depression/Suicide/Self-injury Adverse Events of Special Interest by Category and PT - On Study (Year 1&2) | 
 • Now presents data for Year 1&2 |
| 23.35. | 23.41 | ITT | Adverse Events of Special Interest including Exposure-Adjusted Incidence Rates by Category – On Study (Year 1&2) | 
 • Now presents data for Year 1&2 |
| COVID-19 Pandemic Adverse Events | | | | |

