5.11. On Study

For Year 1, on study is defined as from 1st dose of belimumab to the earliest of:

- Week 52 visit assessment
- Study withdrawal (including LTFU and Death)

However, for subjects that withdraw during Year 1, the on treatment period could end later than the on study period. In this situation the on study period will be reset such that it ends at the same time as the on treatment period.

NOTE: Some subjects who are enrolled toward the end of the enrolment period and withdraw at or near their Week 52 assessment may have some of their Year 1 on study period reported at the end of the study (Section 5.7).

For Year 2, on study is defined as from the Week 52 visit assessment* until the date of study completion or study withdrawal (including LTFU and death).

*Subjects who did not complete week 52 but had not withdrawn prior to Week 52, and have post Week 52 assessments will use scheduled visit date.

For Year 1&2 on study is defined as from the 1st dose of belimumab until the date of study completion or study withdrawal (including LTFU and death).

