8.1.5. Post-Injection Systemic Reactions

Summaries of post-injection systemic reactions that occur on the day of an injection or within 3 days after an injection will be presented by treatment group, by the first six injections and over all injections, and PT for the following:

- Post-Injection Systemic Reactions Adverse Events of Special Interest by Category and PT [T13.33, T23.32].
- Serious Post-Injection Systemic Reactions Adverse Events of Special Interest by Category and PT [T13.34, T23.33].
- Post-Injection Systemic Reactions per Anaphylactic Reaction CMQ broad search (on the day of the injection or within 3 days after the Belimumab injection) by PT in the first six injections [On treatment:T13.35].
- Serious Post-Injection Systemic Reactions per Anaphylactic Reaction CMQ broad search (on the day of the injection or within 3 days after the Belimumab injection) by PT in the first six injections [on Treatment: T13.36].
- Serious Acute Post-Injection Systemic Reactions/Hypersensitivity per GSK Adjudication by PT in the First Six Injections [On Treatment: T13.37].
- Serious Delayed Acute Hypersensitivity Reactions per GSK Adjudication by PT in First Six Injections [On Treatment:T13.38].
- Serious Delayed Non-Acute Hypersensitivity Reactions per GSK Adjudication by PT in First Six Injections [On Treatment: T13.39].
- Post-Injection Systemic Reactions per Anaphylactic Reaction CMQ broad search (on the day of the injection or within 3 days after the Rituximab infusion) by PT [On treatment:T13.40].

8.1.6. Additional Adverse Event Summaries to Assess the Impact of the Coronavirus Disease 2019 (COVID-19) Pandemic

Additional adverse event summaries will be produced to further understand the safety profile and/or impact of the COVID-19 pandemic on safety.

Two listings will be produced to show the number of subjects with a suspected, probable or confirmed COVID-19 infection. The first listing will present data for Year 1 On Treatment (Section 5.12) [L13.26]; the second listing will present data for Years 1 and 2 combined On-Study (Section 5.11) [L23.27]. Both listings will also show the number of subjects who had a COVID-19 diagnosis test performed and the number of subjects with positive, negative, or indeterminate results. The listings will be based on information collected on the COVID-19 Coronavirus Infection Assessment CRF page.

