| 
On-Study Exposure (Years 1&2 Combined)
 
 • Number of days of On-Study exposure will be calculated based on the formula: |

| On-Study Exposure (Years 1&2 Combined) |
|--|
| 
Duration of On-Study Exposure in Days = Date of study completion or withdrawal – First Belimumab injection date + 1
 
 • Only complete dates will be used when calculating duration of study exposure. • Participants who were randomized but did not report a treatment start date will be categorised as having zero days of exposure. |

| Disease Duration |
|--|
| 
When the start day is missing, impute with 01. When the start day and month is missing, impute with 01 January. This will impute the longest possible duration.
 |

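### In the Years 1&2 exposure-adjusted AESI table, post-injection systemic reactions are divided by on-study time, about half of which in Arms A and B falls after planned injections have stopped

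*SAP*

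**What the plan says.** - **Denominator.** RAP Section 8.1.4 defines it as "For Years 1&2 combined: the sum of the total time to the first event or total on-study time* if no event (years". Section 15.6.2 gives the time itself: "Duration of On-Study Exposure in Days = Date of study completion or withdrawal – First Belimumab injection date + 1". Section 5.11 agrees: "For Year 1&2 on study is defined as from the 1st dose of belimumab until the date of study completion or study withdrawal". Neither definition contains a dosing term, so the clock runs the same way in all three arms.
- **Scope.** Of the AESI rate tables, Section 8.1.4 says: "These will present AESI Overall and by each specific category and Preferred Term". The AESI list in that section includes "Post-Injection Systemic Reactions (PISR").
- **Link to injections.** Section 8.1.5 introduces "Summaries of post-injection systemic reactions that occur on the day of an injection or within 3 days after an injection".
- **Dosing.** The protocol synopsis has weekly belimumab "through Week 51 for Arms A and B, and through Week 103 for Arm C". Protocol Section 5.1 makes Weeks 53-104 treatment-free for Arms A and B. Section 7.7.4 allows open-label belimumab to be re-started in that period.
- **On-treatment time.** RAP Section 5.12 treats Arms A and B as off treatment in Year 2. It defines a combined Year 1&2 on-treatment period for Arm C only (to last dose + 28 days), and this rate does not use it.
- **Status of the table.** Section 2.1.7 of the second RAP addendum keeps "Adverse Events of Special Interest including Exposure-Adjusted Incidence Rates by Category" for Year 1&2, on study, as T23.35 (old 23.41). No Years 1&2 PISR rate on injection or on-treatment time is listed.

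**The concern.** A PISR needs an injection to react to. In Year 2 an A/B participant who has not re-started belimumab and takes no leftover doses keeps adding person-time with almost no opportunity for such an event, while an Arm C participant keeps adding both. The label exposure-adjusted invites the reader to assume that the difference in dosing duration has been dealt with, and it has not.

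Protocol Section 3.3.1 names hypersensitivity and injection or infusion reactions as a risk of co-administration. Arm C is the reference for belimumab with standard therapy. A reader who sets the Arm B row beside the Arm C row could be falsely reassured by a low rate that arises because dosing stopped.

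**Working it through.** The documents give no exposure-adjusted rate, so there is no planned figure to reproduce. The check is person-time arithmetic with the RAP's formula, r = 100 × n / e.

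**Days for a participant who completes as planned.** RAP Section 15.3.1 puts Week 52 at Day 365 and Week 104 at Day 729. The last planned injection is therefore Day 358 in A/B (Week 51) and Day 722 in C (Week 103). On-study time is 729 days in every arm.

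| Definition of injection-exposed time | A/B | C |
|---|---|---|
| Last − first + 7 (RAP 6.5) | 364/729 = 0.50 | 728/729 = 1.00 |
| To last injection + 3 days (RAP 8.1.5) | 361/729 = 0.495 | 725/729 = 0.995 |
| To last injection + 28 days (RAP 5.12) | 386/729 = 0.53 | 729/729 = 1.00 (capped) |

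**Re-start.** The documents give no re-start rate. If a fraction f of A/B completers re-start for an average of 26 weeks (assumption), the share is (364 + 182f)/729, which is 0.57 at f = 0.3 and 0.62 at f = 0.5.

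**Constant hazard, 10% one-year incidence (assumption), no dropout or re-start.** The hazard is −ln(0.9) = 0.105 per year.

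- Year 1 person-time per participant = 0.1/0.105 = 0.949 years.
- A/B on-study time = 0.949 + 0.9 × 1 = 1.849 years, so the rate is 10/1.849 = 5.4 per 100 subject-years.
- A/B on injection time: 10/0.949 = 10.5.
- Arm C is 10.5 on either basis. The on-study A/B:C ratio is 5.4/10.5 = 0.51, although the true risk per injection-exposed time is equal.

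**All reactions in the first six weeks, same 10% incidence.** Mean time to an event is about 3 weeks.

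- On-study time in every arm = 0.9 × 2 + 0.1 × 3/52 = 1.806 years. All arms show 5.5, so the ratio is 1.0.
- On injection time, A/B = 10/(0.9 + 0.006) = 11.0 against 5.5 in C, a ratio of about 2.0.

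**Simulation** (400,000 participants per scenario, 10% one-year incidence; all scenario values are assumptions). Factor = A/B on-study rate divided by A/B injection-time rate.

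| Scenario | Constant: factor | A/B:C on study | A/B:C injection time | Early: factor | A/B:C on study | A/B:C injection time |
|---|---|---|---|---|---|---|
| No dropout, no re-start | 0.513 | 0.51 | 0.99 | 0.502 | 1.01 | 2.02 |
| 15% dropout | 0.534 | 0.53 | 0.99 | 0.522 | 1.01 | 1.93 |
| 30% dropout, 15% per year stop belimumab but stay in study | 0.514 | 0.60 | 1.00 | 0.505 | 1.01 | 1.72 |
| 15% dropout, 30% A/B re-start | 0.602 | 0.61 | 1.01 | 0.593 | 0.99 | 1.67 |
| 15% dropout, 50% A/B re-start | 0.647 | 0.64 | 0.99 | 0.640 | 1.00 | 1.56 |

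The Arm C factor is 1.00 throughout, except about 0.86 in the third row. Over one-year incidences of 2-30%, the constant-hazard on-study ratio is 0.51-0.57 without re-start or early stops, and 0.58-0.67 with either. With early reactions it stays at 0.97-1.02.

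**The case against.** The strongest objection is that a B:C ratio of one half needs a constant reaction hazard. The RAP itself allows for early reactions: Section 8.1.5 tabulates the first six injections separately (T13.35-T13.39). The rate counts only first events, so with early reactions the arms have equal numerators and near-equal on-study time, and the displayed ratio is right. Replacing the denominator would then make equal risks look like a ratio of about 1.6-2.0. This stands. It rules out the inference that T23.35 must show half the Arm C rate, and it rules out substituting one denominator for the other.

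Second, the 3-day window does not fit every PISR row. Section 8.1.4 includes adjudicated delayed hypersensitivity, and the category definitions sit in a programme safety plan that is not in these documents. A reader might infer that no PISR can arise in A/B after about Day 361 without re-start or late doses. The documents do not support that for the delayed rows. The dilution hardly changes, however: with a 28-day tail the A/B share is still 0.53.

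Third, other displays help. T13.48 gives Year 1 AESI rates on on-treatment time, when all arms share the weekly schedule. The addendum keeps PISR counts (T23.30, T23.31) and belimumab exposure including re-start (T21.10, T21.11). Safety is descriptive (protocol Section 10.4.2), Arm C is a qualitative reference, and no inferential tests against it are planned (protocol Section 10.2). This limits the importance of the point, but none of it makes on-study time a measure of exposure to injections in T23.35.

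**Conclusion.** The point holds as a limited one. In T23.35 the A/B PISR rate per injection-exposed time is understated by about a third to a half. The half applies to completers with no re-start, and the third to re-start by about 50% of A/B, a figure that is assumed. Arm C is essentially undiluted unless many participants stop belimumab early and stay in the study.

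This dilution does not depend on when reactions occur, but the A/B versus C ratio does: about 0.5-0.67 instead of 1.0 under a constant hazard, and near 1.0 if reactions come almost only with the first injections. The documents do not say which pattern to expect.

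A reader might also infer that the comparison of combination with control is biased. The planned schedule gives no support for that, because A and B share it. Primary and secondary efficacy conclusions are not touched. The change is worth making because it removes a foreseeable misreading of a named safety risk at little cost.

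**What to change.** Keep the on-study rate in T23.35. For the PISR rows, add one of these beside it:

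- a rate per 100 injections; or
- a rate per injection-exposed time, summed over study-treatment, late and re-start doses, with the RAP's last dose + 28 days tail so that delayed reactions are covered.

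Footnote that Arms A and B have no planned belimumab injections in Year 2. The two rates should be read together, since each can mislead on A/B versus C under a different timing of reactions. The other AESI categories can stay on on-study time. The original T23.39 (adverse events leading to belimumab discontinuation, by exposure) needs no change, because it is not in the abridged list.

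The cost is a sentence in the addendum, one further exposure variable from dosing data already needed for T21.10 and T21.11, and a few extra table rows.
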